| 
Concept and Rationale:
 
Approximately 20 percent of unselected patients with advanced non-small cell lung cancer (NSCLC) and progression during or after standard first line chemotherapy will experience tumor response to nivolumab¹⁻⁴. Treatment options for patients who are not responsive to programmed death 1 (PD-1) axis inhibitor therapy are limited, and the mechanisms of primary resistance are poorly understood.
 
The combination of nivolumab and ipilimumab is currently FDA approved for the treatment of advanced melanoma based on superiority to either agent alone⁵. The results of a phase I study evaluating combination therapy with nivolumab and ipilimumab in patients with advanced NSCLC (NCT01454102) were presented at the annual American Society of Clinical Oncology (ASCO) meeting in 2016⁶. Dosing of nivolumab 3 mg/kg every 2 weeks and ipilimumab 1 mg/kg every 6 weeks yielded an objective response rate (ORR) by RECIST v1.1 of 39%, with one-year survival rate of 69% and grade 3-4 treatment-related adverse event rate of 33%. These results prompted an ongoing phase III study comparing this regimen to standard first line chemotherapy, nivolumab monotherapy or combination therapy with chemotherapy and nivolumab for patients with advanced NSCLC (NCT02477826).
 
We propose a trial to evaluate if the addition of ipilimumab to nivolumab after primary resistance to anti-PD-1 axis therapy can lead to objective radiographic tumor regression. It is hypothesized that ipilimumab will enable more effective immune priming in some patients, resulting in the trafficking of tumor-specific cytotoxic T cells to the tumor, as well as depletion of tumor-permissive T regulatory cells. With concurrent nivolumab, PD-1 inhibition in the tumor will enable effective anti-tumor attack by tumor-specific T cells. Serial tumor biopsies and blood collections will allow interrogation of changes in the tumor microenvironment (and periphery) that support this hypothesis.
 
We will primarily enroll patients who have experienced progression of NSCLC after anti-PD-1-axis therapy without initial response to such therapy ('primary resistance'). A smaller cohort of patients with acquired resistance to anti-PD-1 axis therapy (i.e. progression after initial response) will additionally be accrued.
 |
| 
Primary Objective/ Endpoint:
 
 - To determine the objective response rate (ORR) using RECIST v1.1 to nivolumab and ipilimumab when administered in combination to patients with pre-treated advanced |

| |
|--|
| 
NSCLC who have experienced primary resistance to anti-PD-1 axis therapy as their last line of systemic therapy.
 |
| 
Secondary Objective(s)/ Endpoint(s):
 
 - To determine the objective response rate (ORR) using immune related Response Criteria (irRC) to nivolumab and ipilimumab when administered in combination to patients with pre-treated advanced NSCLC who have experienced primary resistance to anti-PD-1 axis therapy as their last line of systemic therapy. - To determine progression-free (RECIST v1.1 and irRC) and overall survival with nivolumab and ipilimumab when administered in combination to patients with pre-treated advanced NSCLC who have experienced primary resistance to anti-PD-1 axis therapy as their last line of systemic therapy. - To determine ORR and progression free survival (PFS) by RECIST v1.1 and irRC, and overall survival, with nivolumab and ipilimumab in patients with pre-treated advanced NSCLC who have experienced acquired resistance to anti-PD-1 axis therapy as their last line of systemic therapy. - To characterize the safety profile of nivolumab and ipilimumab when administered in combination, and feasibility of sequential biopsies, in patients with pre-treated advanced NSCLC who have experienced primary or acquired resistance to anti-PD-1 axis therapy as their last line of systemic therapy. - To evaluate changes in the tumor microenvironment and blood after adding ipilimumab to nivolumab in patients with primary and acquired resistance to anti-PD-1-axis as their last line of systemic therapy. |
| 
Study Design:
 
This a phase II study employing a Simon two-stage design to evaluate the primary endpoint of ORR by RECIST v1.1 to combination therapy with nivolumab 3 mg/kg administered intravenously (IV) every 2 weeks, with ipilimumab 1 mg/kg administered IV every 6 weeks, in patients with advanced NSCLC and primary resistance to anti-PD-1 axis therapy. If there is at least one response or prolonged stability (≥ 24 weeks) using irRC appreciated in the first 10 patients who initiate trial therapy, a total of 40 patients will be enrolled. An additional 10 patients with acquired resistance to anti-PD-1 axis therapy will be enrolled in an exploratory cohort receiving the same therapy.
 
Tumor biopsies (and blood collection for pharmacodynamic studies) will be performed just prior to initiating trial therapy, and 9 to 10 weeks after receiving first dose of trial therapy.
 |
| 
Main Criteria for Inclusion/Exclusion:
 
Inclusion
 
 - Age ≥ 18 years - Histologically or cytologically documented, locally advanced or metastatic (i.e., Stage IIIB not eligible for definitive chemoradiotherapy, Stage IV, or recurrent) NSCLC (per the American Joint Committee /AJCC staging system) - ECOG performance status of 0 to 2 |

- Anti- PD-1 Axis therapy (anti-PD-1 or anti-PD-L1, e.g. nivolumab, pembrolizumab, atezolizumab, durvalumab, avelumab) must be the most recent systemic anti-tumor treatment received in all patients, with documented progressive disease:
 - a. Patients to be enrolled to the primary cohort (primary resistance) must have had progressive disease or stable disease less than 24 weeks as the best clinical response to anti-PD-1-axis therapy.
 - b. Patients to be enrolled to the exploratory cohort (acquired resistance) must have had stable disease for at least 24 weeks, partial response, or complete response as the best clinical response to anti-PD-1-axis therapy, with subsequent progression of disease.
- Chemotherapy naive and treated patients will be eligible, with no limit on number of prior therapies. Patients with NSCLC known to harbor an ALK rearrangement, or EGFR mutation known to be sensitive to FDA approved tyrosine kinase inhibitors (TKI), are only eligible after experiencing disease progression (during or after treatment) or intolerance to an FDA approved EGFR TKI or ALK TKI, respectively:
 - a. Patients with TKI treated EGFR mutant NSCLC harboring the secondary EGFR T790M tumor must have received prior osimertinib.
 - b. Patients with crizotinib treated ALK rearranged NSCLC must have received a next generation ALK inhibitor (e.g. ceritinib, alectinib or brigatinib).
- At least one tumor amenable to incisional, excisional, core or forceps (transbronchial) biopsy. Patients must be willing to undergo tumor biopsies before starting trial therapy, and 9 to 10 weeks after initiation of therapy:
 - a. If the initial biopsy will be excisional, the excised tumor cannot be counted as a target lesion and there must be another lesion amenable to incisional, excisional, core or forceps biopsy. In this scenario, the second biopsy can only be excisional if the lesion to be excised is not a target lesion.
 - b. Cytology tumor specimens (e.g. from fine-needle biopsies, or drainage of pleural/pericardial or ascites fluid) are not acceptable. Biopsies of bone lesions that do not have a soft tissue component are also not acceptable (i.e. decalcified tumor samples are not acceptable).
- Adequate hematologic and end-organ function

Exclusion

- Subjects must not have a history of life-threatening toxicity related to prior anti-PD-1 axis therapy:
 - a. Subjects with history of anti-PD-1 axis therapy toxicities that are unlikely to recur with standard countermeasures (e.g., hormone replacement after adrenal crisis) are eligible.
- Prior treatment with anti-CTLA-4 therapeutic antibodies
- Symptomatic or untreated CNS metastases. Patients with a history of treated asymptomatic CNS metastases are eligible, provided they meet all of the following criteria:
 - a. No evidence of interim progression between the completion of CNS-directed therapy and the start of trial therapy.

| |
|---|
| 
 b. No ongoing requirement for dexamethasone as therapy for CNS disease; anticonvulsants at a stable dose are allowed. c. Completed stereotactic radiosurgery at least 1 week prior to Cycle 1, Day 1 or whole-brain radiation at least 2 weeks prior to Cycle 1, Day 1. - History of leptomeningeal carcinomatosis - Prior palliative radiotherapy outside the CNS within 2 weeks of the first dose of study drug - Treatment with systemic immunosuppressive medications (including but not limited to, dexamethasone at doses > 2 mg daily (or equivalent dose of other corticosteroids), cyclophosphamide, tacrolimus, sirolimus, azathioprine, methotrexate, thalidomide, and antitumor necrosis factor [anti-TNF] agents) within 2 weeks prior to initiating trial therapy (Inhaled or topically applied steroids, and acute and chronic standard-dose NSAIDs are permitted. Replacement steroids are also permitted). |
| 
Intervention and Mode of Delivery:
 
Nivolumab 3 mg/kg IV every 2 weeks and Ipilimumab 1 mg/kg IV every 6 weeks
 |
| 
Duration of Intervention and Evaluation:
 
Combination therapy with ipilimumab and nivolumab will be continued until disease progression or unacceptable toxicity. Patients with progression of disease by RECIST v1.1 without decline in performance status will be allowed to continue trial therapy if their treating physician believes they are deriving clinical benefit from study therapy.
 
Both RECIST v1.1 and immune-related response criteria (irRC) will be used to assess response to therapy. All patients who receive at least one dose each of ipilimumab and nivolumab will be considered evaluable.
 
Tumor response will be based on tumor assessments at screening, every 9 weeks from the first dose (for the first 24 weeks) and thereafter every 12 weeks until investigator-assessed initial disease progression.
 |
| 
Statistical Methods:
 
For the primary endpoint of objective response rate (ORR) by RECIST v1.1 among patients with primary resistance to anti-PD-1-axis therapy, a Simon two-stage design will be employed. The design is based on our intuition for a very low anticipated response rate and not on any specific experimental evidence. The study will terminate early if there are no responses or prolonged stability (≥ 24 weeks) using irRC among the first 10 patients enrolled. Otherwise we will enroll a maximum of 40 patients with primary resistance and reject the null hypothesis of no objective response if we observe 4 or more positive responses. For a null hypothesis with a 5% ORR and alternative with a 19% ORR, this criterion has significance level 0.1 and power greater than 85%. The null and alternative hypothesis rates are not motivated by experimental evidence but rather, are examples of one pair of hypotheses that can be tested using this design.
 
Progression-free survival will be estimated with derivation of the corresponding 95% CI, plotted using the Kaplan-Meier method. Overall survival will be plotted using the Kaplan-Meier method.
 |

Time-to-event endpoints (PFS, OS) will be analyzed using the Kaplan-Meier plots. We will correlate OSS and PFS with ORR using Cox proportional hazards regression methods. No formal statistical analyses will be conducted on the 10 additional patients with acquired resistance, though the finding of immune related response in 1 or more patients would be unexpected, and should prompt further study.

Funding, Regulatory, and Feasibility Issues:

- Ipilimumab and nivolumab will be supplied by Bristol Myers Squibb Company.
- Bristol Myers Squibb Company will provide additional trial funding, including funding of serial biopsies.
- IND for trial therapy to be held by [name].

Patient Acceptability/Ethics and Consent Issues:

None anticipated

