8. CRITERIA FOR RESPONSE

Anti-tumor activity: data on objective response, progression free survival, and duration of response will be listed for all patients in the study and summarized overall.

Objective response is defined as a complete or partial response, as determined by investigator assessment using RECIST v1.1 and irRC (see appendix 3 and 4) and confirmed by repeat assessments ≥ 4 weeks after initial documentation. Patients not meeting these criteria, including patients without any post baseline tumor assessment, will be considered non-responders in the analysis of objective response.

Duration of objective response will be analyzed for the subset of patients who achieved an objective response. Duration of response is defined as the time from the initial complete or partial response to the time of disease progression or death, whichever occurs first. If a patient does not experience death or disease progression before the end of the study, duration of response will be censored at the day of the last tumor assessment. If no tumor assessments were performed after the date of the first occurrence of a complete or partial response, duration of objective response will be censored at the date of the first occurrence of a complete or partial response plus 1 day.

Progression-free survival is defined as the time from the first day of nivolumab treatment until progression of disease using RECIST v1.1 and irRC (see appendix 3 and 4). If a patient has not experienced progressive disease or death, PFS will be censored at the day of the last tumor assessment. Patients with no post baseline tumor assessments will be censored at the date of first study treatment plus 1 day.

[figure not shown]
Overall survival is defined as the time from the first day of treatment until death from any cause. If a patient has not experienced death, OS will be censored at the day of last follow-up.

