Appendix 4: Immune-Related Response Criteria

INTRODUCTION

Increasing clinical experience indicates that traditional response criteria (e.g., Response Evaluation Criteria in Solid Tumors, Version 1.1 [RECIST v1.1] and World Health Organization [WHO]) may not be sufficient to characterize fully activity in the new era of target therapies and/or biologics. In studies with cytokines, cancer vaccines, and monoclonal antibodies, complete response, partial response, or stable disease has been shown to occur after an increase in tumor burden as characterized by progressive disease by traditional response criteria. Therefore, conventional response criteria may not adequately assess the activity of immunotherapeutic agents because progressive disease (by initial radiographic evaluation) does not necessarily reflect therapeutic failure. Long-term effect on the target disease must also be captured. The immune-related response criteria¹⁹ (irRC) are criteria that attempt to do that by enhancing characterization of new response patterns that have been observed with immunotherapeutic agents (i.e., ipilimumab). (Note: The irRC only index and measurable new lesions are taken into account.)

GLOSSARY

| Term | Definition |
|--------------|---|
| SPD | sum of the products of the two largest perpendicular diameters |
| Tumor burden | $SPD_{\text{index lesions}} + SPD_{\text{new, measurable lesions}}$ |
| Nadir | minimally recorded tumor burden |
| irCR | immune-related complete response |
| irPD | immune-related progressive disease |
| irPR | immune-related partial response |
| irSD | immune-related stable disease |
| irBOR | immune-related best overall response |

BASELINE ASSESSMENT USING irRC

Step 1. Identify the index lesions (five lesions per organ, up to ten visceral lesions and five cutaneous lesions).

Step 2. Calculate the SPD of all of these index lesions:

$$SPD = \sum_i (\text{Largest diameter of lesion } i) \times (\text{Second largest diameter of lesion } i).$$

POST-BASELINE ASSESSMENTS USING irRC

Step 1. Calculate the SPD of the index lesions.

Step 2. Identify new, measurable lesions ($\geq 5 \times 5$ mm; up to five new lesions per organ: five new cutaneous lesions and ten visceral lesions).

Step 3. Calculate the SPD of the new, measurable lesions.

Step 4. Calculate the tumor burden:

$$\text{Tumor burden} = \text{SPD}_{\text{index lesions}} + \text{SPD}_{\text{new, measurable lesions}}$$

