Step 5. Calculate the change in tumor burden relative to baseline and the change in tumor burden relative to nadir.

Step 6. Derive the overall response using the table below.

| Overall Response | Criterion |
|------------------|---|
| irCR | Complete disappearance of all lesions (whether measurable or not, and no new lesions) confirmed by a repeat, consecutive assessment ≥ 4 weeks from the date first documented |
| irPR | Decrease in tumor burden $\geq 50\%$ relative to baseline confirmed by a consecutive assessment ≥ 4 weeks from the date first documented |
| irSD | Criteria for irCR, irPR, and irPD are not met; does not require confirmation |
| irPD | Increase in tumor burden $\geq 25\%$ relative to nadir confirmed by a consecutive assessment ≥ 4 weeks from the date first documented |

irCR = immune-related complete response; irPD = immune-related progressive disease; irPR = immune-related partial response; irSD = immune-related stable disease.

DETERMINATION OF irBOR

Once a patient has completed all tumor assessments, his/her irBOR may be determined:

| Condition | irBOR |
|---|-------|
| At least one irCR | irCR |
| At least one irPR and no irCR | irPR |
| At least one irSD and no irCR and no irPR | irSD |
| At least one irPD and no irCR, no irPR, and no irSD | irPD |

irBOR = immune-related best overall response; irCR = immune-related complete response; irPD = immune-related progressive disease; irPR = immune-related partial response; irSD = immune-related stable disease.

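### Cox regression of OS and PFS on response has no landmark or time-dependent term; fitted as a fixed covariate, response would look protective even with no true effect

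*Combined protocol and SAP*

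**What the plan says.** The synopsis (Statistical Methods) commits to the analysis: "We will correlate OSS and PFS with ORR using Cox proportional hazards regression methods". Section 9 adds only that the secondary analyses correlate ORR, time-to-event measures and the Section 7 metrics. Neither place says how response enters the model.

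The definitions that matter are these:

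- **Time origin (Section 8).** "Overall survival is defined as the time from the first day of treatment until death from any cause". "Progression-free survival is defined as the time from the first day of nivolumab treatment".
- **Response (Section 8).** A complete or partial response must be "confirmed by repeat assessments ≥ 4 weeks after initial documentation". Patients who do not meet the definition, "including patients without any post baseline tumor assessment, will be considered non-responders"; the sentence limits this rule to the analysis of objective response.
- **Scans (synopsis, Duration of Intervention and Evaluation).** Assessments are "every 9 weeks from the first dose (for the first 24 weeks) and thereafter every 12 weeks". The imaging row of the Section 5.4 calendar puts them at week 9, week 18 and every 12 weeks after that.
- **Criterion.** The synopsis introduces ORR as ORR by RECIST v1.1. irRC is a separate secondary criterion. Appendix 4 requires confirmation there too: irPR is a decrease "relative to baseline confirmed by a consecutive assessment" at least 4 weeks later.

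Section 9 has two further sentences on method. One names Cox regression for relating markers to ORR as well as to PFS. The other says the Kaplan-Meier plots will be prepared by RECIST v1.1 and by irRC and tested by log-rank, without naming the groups compared.

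**The concern.** Confirmed response is learned during follow-up, while the survival clocks start on day 1. A fixed covariate treats it as known on day 1. Nobody can then die, or progress by the same criterion, as a responder before confirmation, so every earlier event falls in the non-responder group. The HR is pulled below 1 by construction, more for PFS than for OS because more PFS events come early.

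At stake is a reported statement that responders live longer, made from a single-arm trial and partly or wholly produced by the coding of the covariate. No trial decision depends on it.

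**Working it through.** The plan gives no figure for this analysis, so there is nothing to reproduce. The check is a calculation with no true effect.

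**1. Earliest confirmation.** First scan at week 9, plus 4 weeks, gives week 13 if an extra scan is done. On scheduled scans only, a week-9 response is confirmed at week 18 and a week-18 response at week 30 (18 + 12).

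**2. Assumptions.** Event times are exponential and independent of response. OS medians are 8 to 12.2 months (background figures in Sections 2.1) and the PFS median is 3.9 months (Table 2.2.2, first-line combination arm). The plan states no expected OS or PFS for its own population. At 4.345 weeks per month the medians are 34.8, 53.0 and 16.9 weeks. The 60:40 split between weeks 18 and 30 is assumed.

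**3. Share of events before week 13**, 1 − 2^(−13/median):

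- OS: 1 − 2^(−13/34.8) = 23%; 1 − 2^(−13/53.0) = 16%.
- PFS: 1 − 2^(−13/16.9) = 41%.

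**4. Responders.** An observed responder is a latent responder still event-free at confirmation week c. To observe 10% (4 of 40), the latent rate is 0.10 / 2^(−c/median). For OS at week 13 that is 0.10/0.772 = 13% (8 months) or 0.10/0.844 = 12% (12.2 months).

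**5. Large-sample Cox HR, fixed covariate, true HR 1.00, 10% responders:**

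| Endpoint and follow-up | Confirmed week 13 | 60:40 weeks 18 and 30 |
|---|---|---|
| OS, 104 weeks | 0.74-0.79 | 0.61-0.66 |
| OS, 208 weeks | 0.77-0.83 | 0.66-0.73 |
| OS, complete | 0.77-0.84 | 0.66-0.75 |
| PFS, 104 weeks, progression seen continuously | about 0.6 | 0.47 |

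With progression recorded only at scans, the PFS HR is 0.61-0.74 and 0.47-0.52, depending on the handling of ties and on whether the week-13 scan can detect progression.

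**6. False findings for responders**, n = 40, 104 weeks, assumed threshold z < −1.96 (nominal 2.5%), Wald to log-rank:

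| Endpoint, observed responders | Week 13 | 60:40 |
|---|---|---|
| OS, 5% | 0-1.5% | 0.2-2.9% |
| OS, 10% | 0.7-3.2% | 1.7-6.4% |
| OS, 19% | 3.3-8.2% | 7.4-19.5% |
| PFS, 10% | 1.5-11% | 10-30% |

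**7. Same data, response switched on at confirmation.** The OS HR is 0.99-1.02. The PFS HR is 0.99-1.01 with continuous progression or scheduled confirmation. If an extra week-13 confirmation scan also detects progression, the PFS HR stays at 0.85-0.89, because responders are scanned more often. Switching at the next scheduled scan then gives 1.00. Switching at first documentation does not cure the bias: OS 0.76-0.91 (9.2-month median), PFS 0.58-0.86.

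**8. Section 9 wording.** ORR is a yes/no outcome with no event time, so Cox regression does not apply to it. RECIST and irRC curves come from the same patients, so a log-rank test between them lacks independent groups; for OS the two curves are identical, since OS does not depend on the response criterion.

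**The case against.** **The plan does not specify a fixed covariate.** Cox methods include time-dependent covariates, so a reader who infers that a biased analysis is planned goes beyond the text. This stands. What remains is that the ordinary fit is the default reading and nothing in the plan excludes it.

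**The size depends on borrowed inputs.** This also stands. Section 4.7 follows survival until death, so 104 weeks alone would overstate the OS bias; the longer follow-up rows show it shrinking without disappearing. The PFS median comes from first-line patients. The scan model omits the 9-weekly imaging after treatment discontinuation in Section 5.3. For PFS, a null in which progression is independent of response is artificial, because both come from the same lesion measurements.

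**The harm to OS inference is small at low response rates.** Largely right. The plan anticipates a very low rate, and at 5-10% responders the OS test rarely exceeds its nominal level by much. The point estimate is still biased.

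**The response criterion is not really open.** Mostly right: the synopsis introduces ORR by RECIST v1.1. If irRC response were paired with RECIST PFS, the PFS argument would hold only in part, because Appendix 4 notes that "complete response, partial response, or stable disease has been shown to occur after an increase in tumor burden". For OS the guaranteed time remains under either criterion.

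**The non-responder rule is limited to the analysis of objective response.** True, but the bias does not need that rule. A patient who dies before confirmation cannot be a confirmed responder.

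**Conclusion.** The point holds as a conditional one. If confirmed response is fitted as a fixed covariate from first treatment, the HR favours responders with no true effect. The direction follows from the plan's own definitions, with response and PFS taken by the same criterion. The size is illustrative and rests on the exponential times, medians, confirmation timing and follow-up listed above: at 10% responders, OS HR about 0.61-0.84 and PFS HR about 0.6 or 0.47.

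A reader might infer that the trial's main result is compromised, or that a false OS finding is likely. Neither is supported. The primary test of 4 or more responses in 40 does not use this model, the analysis is not among the listed objectives, and excess false-positive OS tests at 5-10% responders are mostly small or absent. The two Section 9 sentences are separate wording defects and stand on the text alone. This should be corrected, at low severity.

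**What to change.** **Response and survival.** State that confirmed response by RECIST v1.1 enters the Cox models as a time-dependent covariate that switches on at the confirmation date, not at first documentation, and that PFS uses the same criterion. For PFS, add a sensitivity analysis that switches at the next scheduled scan when confirmation came from an unscheduled one.

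**Landmark.** Use it as a sensitivity check with a stated time and tie rule. At week 18 it would lose 1 − 2^(−18/16.9) = 52% of patients for PFS (about 19 of 40 left) and 21-30% for OS (28-32 left). Under the 60:40 split it would count 29-36% of responders as non-responders.

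**Section 9.** Relate markers to ORR with a method for a binary outcome, such as exact logistic regression or a rank test, and keep Cox regression for PFS. Show RECIST and irRC curves descriptively, without a log-rank test. If responders versus non-responders was meant, use the time-dependent analysis instead.

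**Cost.** A few sentences and slightly different code; no extra patients or data, since scan dates are already collected. The price is imprecision. With about 4 responders the simulated standard error of the log HR for OS is 0.62-0.63, so the 95% interval runs from the HR divided by about 3.4 to the HR multiplied by about 3.4 (exp(1.96 × 0.62) = 3.37; exp(1.96 × 0.63) = 3.44). The OS test is conservative: 0.5-1.4% against 2.5%.
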